6.1.3. Prior and Concomitant Medications

Prior and concomitant medications will be coded using GSK Drug coding dictionary, summarized, and listed using generic term, verbatim text, and indication. Separate summaries of prior and concomitant medications will show the number and percentage of participants in the ITT and micro-ITT NTF-S Populations (and micro-ITT NTF-S (IA Set) Population (for concomitant medications only) if the study stops for efficacy) taking each prior and concomitant medication by corresponding Anatomical Therapeutic Chemical (ATC) classification Level 1 (Body System) information. The summary of prior medications will include a separate summary of prior antibiotic medications. The summary of concomitant medications will display separate summaries for systemic concomitant medications, non-systemic concomitant medications, systemic antibiotics taken for the disease under study (started on/after Study Day 1), systemic antibiotics taken for another disease/condition (started on/after Study Day 1), and prohibited (non-antibiotic) medications.

An antibiotic is considered systemic if the route is oral, subcutaneous, intramuscular, intravenous, or rectal.

All prior and concomitant medications, as well as prior and concomitant antibiotic medications for uUTI, will be provided in separate Listings.

6.1.4. Medical History and Current Medical Conditions

Medical history and current medical conditions will be summarized and displayed with the number and percentage of participants for each body system for ITT and micro-ITT NTF-S Populations (and micro-ITT NTF-S (IA Set) Population if the study stops for efficacy). General medical history, previous *Clostridium difficile* infection, and liver/cardiovascular related medical conditions will be summarized separately in Tables and Listings. A distinct summary Table will also be produced for history of previous uncomplicated UTIs during the past 3 months, past 3-6 months, past 6-12 months, and past 5 years, and pre-existing conditions with similar symptoms in past 12 months for the ITT and micro-ITT NTF-S Populations (and micro-ITT NTF-S (IA Set) Population if the study stops for efficacy). All data will be listed.

6.1.5. Treatment Exposure

Treatment exposure will be summarized by treatment group for the Safety and micro-ITT NTF-S Populations (and micro-ITT NTF-S (IA Set) Population if the study stops for efficacy). The summary will include duration of treatment (days), the number of doses administered, number of tablets/capsules, average daily dose, cumulative actual dose, and compliance rate. The number of participants with <80%, ≥80%— <100%, and 100%

compliance rate will also be summarized. Dose administration for all participants will be displayed in the Listing.

Compliance rate (%) will be calculated as:

- Gepotidacin/gepotidacin placebo:

$$\frac{\text{total number of tablets taken}}{20} * 100\%$$

- Nitrofurantoin/nitrofurantoin placebo:

$$\frac{\text{total number of capsules taken}}{10} * 100\%$$

The details of data displays are presented in [Appendix 9](#).

7. EFFICACY ANALYSES

7.1. Primary Efficacy Analyses

The primary clinical question of interest is: what is the treatment effect on therapeutic success rate after 5 days treatment with gepotidacin 1500 mg twice daily compared to 5 days treatment with nitrofurantoin 100 mg twice daily in participants with acute cystitis who have a qualifying uropathogen at Baseline that is susceptible to nitrofurantoin regardless of treatment discontinuation for any reason. Receipt of systemic antimicrobials impacts the endpoint definition (see [Table 6](#), [Table 7](#) and [Table 8](#)). Further details on the primary estimand are given in Section [2.2.1](#).

7.1.1. Endpoint / Variables

7.1.1.1. Therapeutic Response at TOC

The primary efficacy endpoint is therapeutic response (combined per participant microbiological and clinical response) at the Test of Cure (TOC) Visit. Therapeutic response is a dichotomous measure of overall efficacy response, either a success or failure, and will be determined programmatically. A therapeutic success refers to participants who have been deemed both a participant level “microbiological success” and a “clinical success”. All other combinations will be deemed failures for therapeutic response. The detailed definitions of microbiological and clinical response are given in [Table 6](#), [Table 7](#), and [Table 8](#).

7.1.1.2. Microbiological Outcome and Response at TOC

- Only those participants who have a qualifying uropathogen (Section [5.2.1](#)) identified at Baseline will be evaluated for microbiological outcome and response by baseline qualifying uropathogen for the primary efficacy endpoint.

- The microbiological success at the uropathogen level is defined as a reduction of bacterial count to $<10^3$ CFU/mL for a specific qualifying uropathogen recovered at Baseline without the participant receiving any other systemic antimicrobials before the TOC Visit (started on/after Study Day 1). The criteria of microbiological outcome and response are shown in [Table 6](#).
- Participant level microbiological response is a measure of the combined “by uropathogen” response(s). Per-participant level microbiological success refers to participants who have been deemed “microbiological success” for all of their qualifying baseline uropathogen(s) microbiological responses. All other combinations are deemed failures for per-participant level microbiological response. Participant-level microbiological outcome and response definitions at TOC are shown in [Table 7](#).

Table 6 Microbiological Outcome and Response by Baseline Qualifying Uropathogen at the TOC Visit - uropathogen level

Defining Criteria	Outcome	Response
Participants considered microbiological failures at the TOC Visit will also be considered microbiological failures at the Follow-up Visit.		
A quantitative urine culture taken at the TOC Visit shows reduction of the qualifying uropathogen recovered at Baseline to $<10^3$ CFU/mL without the participant receiving other systemic antimicrobials before the TOC Visit	Microbiological eradication	Microbiological success
A quantitative urine culture taken at the TOC Visit shows that the qualifying uropathogen recovered at Baseline, and which was also shown to persist or is unable to determine at the On-therapy Visit, grows $\geq 10^3$ CFU/mL without the participant receiving other systemic antimicrobials before the TOC Visit	Microbiological persistence	Microbiological failure
A quantitative urine culture taken at the TOC Visit shows that the qualifying uropathogen recovered at Baseline, and which was also shown to be eradicated at the On-therapy Visit, grows $\geq 10^3$ CFU/mL without the participant receiving other systemic antimicrobials before the TOC Visit	Microbiological recurrence	Microbiological failure
(1) The TOC urine culture result is missing or (2) The participant received other systemic antimicrobials before the TOC Visit	Unable to determine	Microbiological failure

CFU=colony-forming units; TOC=Test-of-Cure.

Table 7 Participant-level microbiological outcome and response at the TOC Visit

Defining Criteria	Outcome	Response
All qualifying baseline uropathogens have a microbiological outcome of eradication at TOC	Microbiological eradication	Microbiological success
At least one qualifying baseline uropathogen has an outcome of persistence at TOC	Microbiological persistence	Microbiological failure
At least one qualifying baseline uropathogen has an outcome of recurrence and none have an outcome of persistence at TOC	Microbiological recurrence	Microbiological failure
All qualifying baseline uropathogen outcomes are unable to determine at TOC	Unable to determine	Microbiological failure

TOC=Test of Cure

7.1.1.3. Clinical Outcome and Response at TOC

- Clinical signs and symptoms of acute cystitis will be recorded by site staff based on participant interview using the following scoring system:

Clinical Signs and Symptoms	None	Mild Symptom is easily tolerated, causing minimal discomfort and not interfering with everyday activities	Moderate Symptom is sufficiently discomforting to interfere with normal everyday activities	Severe Symptom prevents normal everyday activities
	SCORE 0	SCORE 1	SCORE 2	SCORE 3
Dysuria				
Frequency				
Urgency				
Lower abdominal or suprapubic pain				

- The clinical signs and symptoms include dysuria, frequency, urgency, and lower abdominal or suprapubic pain. Each of the signs and symptoms will be scored from 0 to 3.
- At Baseline, the participant must present with at least 2 signs and symptoms and have a total cumulative symptom score ≥ 2 . The total cumulative symptom score is derived by summing the score for each individual sign and symptom. If any individual sign and symptom scores are missing, then total symptom score will also be missing. At TOC, success is defined as normal presentation of signs and symptoms with a total cumulative symptom score of zero. If the participant is missing baseline assessment, they will be considered ‘Unable to determine’ for outcome, and ‘Clinical failure’ for response at the respective visit.

- The clinical outcome and response will be programmatically determined by comparing the total scores of the signs and symptoms of acute cystitis at the TOC Visit to those present at Baseline as shown in [Table 8](#).

Table 8 Clinical Outcome and Response at the TOC Visit

Defining Criteria	Outcome	Response
Test-of-Cure Visit		
Resolution of signs and symptoms of acute cystitis present at Baseline (and no new signs and symptoms), without the participant receiving any other systemic antimicrobials before the TOC Visit	Clinical resolution	Clinical success
Improvement in total symptom scores from Baseline, but not complete resolution, without the participant receiving other systemic antimicrobials before the TOC Visit	Clinical improvement	Clinical failure
Worsening or no change in total symptom scores from Baseline or the participant received other systemic antimicrobials for the current infection before or on the date of the TOC Visit	Clinical worsening	Clinical failure
(1) The baseline score is missing or (2) The TOC assessment is missing or (3) The participant received other systemic antimicrobials not for the current infection before the TOC Visit (unless clinical worsening outcome criteria were met)	Unable to determine	Clinical failure

TOC=Test-of-Cure.

If participant took both other systemic antimicrobials for the current infection on or before the date of the TOC Visit (started on/after Study Day 1), and other systemic antimicrobials not for the current infection before the date of the TOC Visit (started on/after Study Day 1), then participant will be derived as ‘Clinical worsening’.

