8.1.3. Clinical Evaluation

8.1.3.1. Clinical Signs and Symptom Scores, Clinical Outcomes, and Clinical Response

Clinical signs and symptoms of acute cystitis will be recorded based on participant interview per the SoA (Section 1.3) using the scoring system and instructions in [Appendix 6](#). At Baseline, the participant must present with at least 2 signs and symptoms and have a total cumulative symptom score ≥ 2 . At TOC, success is defined as normal presentation of signs and symptoms with a total cumulative symptom score of zero and no new signs and symptoms of the infection under study.

A study physician or otherwise appropriately medically trained staff will determine the individual clinical signs and symptoms scores for acute cystitis ([Appendix 6](#)) at the On-therapy, TOC, and Follow-up Visits. The same scorer will be used at all assessment

time points for each participant, on all occasions, whenever possible. The score will be used to programmatically determine the clinical outcome at the On-therapy Visit (Table 9) and the clinical outcome and response (success or failure) at the TOC Visit (Table 10) and the Follow-up Visit (Table 11).

Table 9 Clinical Outcome at the On-Therapy Visit

Defining Criteria	Outcome^a
Resolution of signs and symptoms of acute cystitis present at Baseline (and no new signs and symptoms), without the participant receiving other systemic antimicrobials before the On-therapy Visit	Clinical resolution
Improvement in total symptom scores from Baseline, but not complete resolution, without the participant receiving other systemic antimicrobials before the On-therapy Visit	Clinical improvement
Worsening or no change in total symptom scores from Baseline or the participant received other systemic antimicrobials for the current infection prior to or on the date of the On-therapy Visit	Clinical worsening
1) The Baseline score is missing, or 2) The On-therapy assessment is missing, or 3) The participant received other systemic antimicrobials not for the current infection prior to the assessment (unless clinical worsening outcome criteria were met)	Unable to determine

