- a. A study physician or otherwise appropriately medically trained staff will determine the individual clinical signs and symptoms scores for acute cystitis (Appendix 6), which will then be used to programmatically determine the clinical outcome. The same scorer will be used at all assessment time points for each participant, on all occasions, whenever possible.

Table 10 Clinical Outcome and Response at the Test-of-Cure Visit

Defining Criteria	Outcome^a	Response
Resolution of signs and symptoms of acute cystitis present at Baseline (and no new signs or symptoms), without the participant receiving other systemic antimicrobials before the TOC Visit	Clinical resolution	Clinical success
Improvement in total symptom scores from Baseline, but not complete resolution, without the participant receiving other systemic antimicrobials before the TOC Visit	Clinical improvement	Clinical failure
Worsening or no change in total symptom scores from Baseline or the participant received other systemic antimicrobials for the current infection before or on the date of the TOC Visit	Clinical worsening	Clinical failure
1) The Baseline score is missing, or 2) The TOC assessment is missing, or 3) The participant received other systemic antimicrobials not for the current infection prior to the assessment (unless clinical worsening criteria were met)	Unable to determine	Clinical failure

TOC = Test-of-Cure

- a. A study physician or otherwise appropriately medically trained staff will determine the individual clinical signs and symptoms scores for acute cystitis ([Appendix 6](#)), which will then be used to programmatically determine the clinical outcome. The same scorer will be used at all assessment time points for each participant, on all occasions, whenever possible.

Table 11 Clinical Outcome and Response at the Follow-up Visit

Defining Criteria	Outcome^a	Response
Resolution of signs and symptoms of acute cystitis demonstrated at the TOC Visit persist at the Follow-up Visit (and no new signs and symptoms), without the participant receiving other systemic antimicrobials before the Follow-up Visit	Sustained clinical resolution	Clinical success
Resolution of signs and symptoms of acute cystitis present at Baseline (and no new signs or symptoms), after clinical failure at TOC, without the participant receiving other systemic antimicrobials before the Follow-up Visit	Delayed clinical resolution	Clinical failure

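### One blank baseline symptom item turns an observed clinical success at TOC into a primary-endpoint failure, although no value of that item could change the response

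*SAP*

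**What the plan says.** SAP Section 7.1.1.3 scores dysuria, frequency, urgency and lower abdominal or suprapubic pain from 0 to 3 each and sums them. Four of its statements bear on this point:

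- Missing items: "If any individual sign and symptom scores are missing, then total symptom score will also be missing".
- Success: "At TOC, success is defined as normal presentation of signs and symptoms with a total cumulative symptom score of zero".
- Missing baseline: "If the participant is missing baseline assessment, they will be considered" unable to determine for outcome and a clinical failure for response.
- Derivation: "The clinical outcome and response will be programmatically determined by comparing the total scores of the signs and symptoms" at TOC with those at Baseline, as laid out in Table 8.

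The success row of Table 8 starts "Resolution of signs and symptoms of acute cystitis present at Baseline (and no new signs and symptoms" and also requires that no other systemic antimicrobial was received before TOC. The last row gives unable to determine, hence clinical failure, when "1) The baseline score is missing or (2) The TOC assessment is missing", or after an antimicrobial for another infection.

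Protocol Section 8.1.3.1 defines TOC success as a normal presentation "with a total cumulative symptom score of zero and no new signs and symptoms of the infection under study". The last row of its Table 10 reads "1) The Baseline score is missing, or 2) The TOC assessment is missing" and leads to the same result. Table 11 in each document carries the same condition to Follow-up. The rule that one blank item voids the total appears only in the SAP. Under protocol Section 8.1.1 and SAP Section 7.1.1.1, a clinical failure is a therapeutic failure whatever the culture shows.

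**The concern.** A participant whose TOC assessment is complete and symptom-free is recorded as a failure because of a gap in a pretreatment form. Nothing in the estimand asks for this. Its intercurrent events are treatment discontinuation and use of systemic antimicrobials, and an incomplete baseline form is neither. Protocol Section 9.4.2 imputes failure for absent or missing data at TOC, and SAP Section 11.5.2 ties missing-as-failure to the corresponding visit. Only the baseline rule reaches back to overturn an observed TOC result.

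At stake are a slightly lower observed success rate, some power, and, because this is a noninferiority trial, a slight pull of any true difference towards zero.

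**Working it through.** **1. The chain of rules.** One baseline item blank → baseline total missing (SAP 7.1.1.3) → baseline score missing (Table 8, last row) → unable to determine → clinical failure → therapeutic failure.

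**2. Can the blank item matter?** Suppose at least two baseline symptoms are recorded and no other systemic antimicrobial was taken. Let the blank item be b = 0, 1, 2 or 3. The recorded items sum to at least 2, so the true baseline total is at least 2 for every b.

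| TOC total | Outcome if b were known | Response for every b | Response under the rule |
|---|---|---|---|
| 0 | Resolution: all four items absent, so nothing persists and nothing is new | Success | Failure |
| above 0 | Improvement or worsening, depending on b | Failure | Failure |

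The baseline value separates improvement from worsening, and both are failures. It never decides success. In the first line of the table the participant satisfies the success row and the unable-to-determine row of Table 8 together.

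**3. Can the case arise?** Yes. The entry requirement of two symptoms and a total of at least 2 can be met with three items recorded.

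**4. Does another planned analysis recover it?** Not as a success. Multiple imputation and the tipping-point analysis (SAP 7.1.6.2) cover only TOC data missed because of COVID-19 and TOC samples without a result; other missing data stay failures. The ME-TOC and CE-TOC populations (SAP Section 4) need a non-missing baseline score, so they drop her.

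**5. Size.** Inputs: 76% success in both arms, margin −10 points, 1:1 allocation, maximum 884 (protocol 9.2.1); looks at 530 and 884, efficacy Z 2.104 and 2.23, non-binding futility Z 0.854 (SAP Table 2).

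The plan's own figure first:

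- SE(N) = √[2 × 0.76 × 0.24 / (N/2)], which is 0.0371 at 530 and 0.0287 at 884.
- Mean Z = 0.10/SE, which is 2.70 and 3.48; correlation √(530/884) = 0.774.
- Power = P(Z₁ > 2.104) + P(0.854 < Z₁ < 2.104, Z₂ > 2.23) = 90.2%, against the stated 90%. One-sided alpha is 0.0250.

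Now let f be the share of participants affected, equal in both arms and unrelated to outcome. The documents do not give f; the values below are assumptions. The observed rate is 0.76 × (1 − f), and the number of successes lost is 884 × f × 0.76.

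| f | Successes lost | Observed rate | Power |
|---|---|---|---|
| 0 | 0 | 76.0% | 90.2% |
| 0.5% | 3.4 | 75.6% | 89.9% |
| 1% | 6.7 | 75.2% | 89.5% |
| 2% | 13.4 | 74.5% | 88.9% |

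A true difference of −10 points (66% against 76%) is observed as −10 × (1 − f): −9.9 at f = 1% and −9.8 at f = 2%. The one-sided type I error, with futility not applied, goes from 0.0250 to 0.0268 and 0.0286.

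**The case against.** The strongest reply is that this is a prespecified, symmetric missing-as-failure rule with one answer for the programmer. That stands. A reader might infer that the SAP contradicts the protocol, or that the response is left undetermined. Neither holds: the two tables match, and the missing-baseline sentence resolves the row overlap as failure.

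The case is also likely to be rare, and that stands too. Protocol Section 8 requires baseline evaluations to be completed and reviewed for eligibility. SAP Section 5.2 takes the latest non-missing predose value, including unscheduled assessments, and accepts any Day 1 symptom assessment, so a second complete Day 1 record can fill the gap.

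The wording leaves some room. The SAP text speaks of a missing baseline assessment and Table 8 of a missing baseline score. If only a wholly absent assessment were meant, one blank item would not trigger failure. The any-item rule, together with derivation from totals, makes the stricter reading the natural one.

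Two further inferences go too far. One is that the rule favours an arm. The gap normally precedes treatment in a randomized double-blind trial, so no systematic imbalance is expected. The other is that the baseline should never matter once the TOC total is zero. Success means resolution of symptoms present at Baseline; for a woman with no baseline symptom record, there is nothing documented to resolve, and calling her a success is debatable.

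The reply that success is defined relative to Baseline does not rescue the one-blank-item case. There the recorded items document symptoms, and all four are absent at TOC.

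**Conclusion.** The point holds for a partly recorded baseline that still shows at least two symptoms, with a TOC total of zero and no other systemic antimicrobials. Such a participant is misclassified on the primary endpoint, and no planned analysis in the primary population corrects it.

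The effect is probably very small. Under the assumed range of 0.5% to 2%, power falls by 0.3 to 1.3 points and the success rate by 0.4 to 1.5 points. These figures rest on an unsupported rate, the same in both arms and independent of outcome, and on no substitute Day 1 assessment being available. Severity: minor.

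**What to change.** Before unblinding, amend SAP Tables 8 and 11 and protocol Tables 10 and 11 as follows:

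- If the baseline score is only partly missing and the recorded items show at least two symptoms, do not apply the missing-baseline condition when the visit total is zero and no other systemic antimicrobials were taken. Derive the response from the remaining criteria. At Follow-up this gives sustained or delayed resolution according to the TOC response.
- Keep unable to determine and clinical failure when the baseline assessment is wholly absent, and limit the matching sentence in SAP Section 7.1.1.3 to that case. This also settles the difference between score and assessment.
- List the change in SAP Section 2.1.

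The cost is a small edit to the endpoint derivation in both documents. No new data are needed.

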7.1.2. Summary Measure

Difference in the therapeutic success rate in the gepotidacin and nitrofurantoin treatment groups (gepotidacin 1500 mg BID – nitrofurantoin 100 mg BID).

